## Protocol

Title: Age-Related Effects of THC (“Effects of drugs on behavior – ART” on the consent form)

Principal Investigator: [name], Ph.D.

Co-Investigators: [name]. and [name].

**Objectives:** **1)** To determine whether adolescents (defined here as ages 18-20) are at greater risk to acute oral 7.5 and 15 mg  $\Delta 9$ -tetrahydrocannabinol (THC) intoxication than adults (defined here as ages 30 to 40), **2)** to develop a sensitive behavioral measure to detect intoxication levels of THC, and **3)** to determine whether age-related drug effects are detectable using electroencephalography (EEG).

**Background:** Increased accessibility to cannabis and its primary psychoactive constituent THC has raised public health concerns. One major concern surrounds the potential risks associated with acute THC intoxication and who might be most at risk. A second major concern is the need to develop sensitive measures that can detect THC intoxication after recent use and enable robust comparisons of intoxication to determine sources of risk. One potential source of risk is age, specifically during the period of adolescence. Preclinical studies indicate that adolescent rats are more sensitive to the acute effects of THC than adults (Cha et al., 2006; Quinn et al., 2008; Wiley et al., 2007), findings that are related to the brain during adolescence. Specifically, during this critical neurodevelopmental period, expression levels of the receptor that THC activates – the cannabinoid receptor (CB1R) – are more prevalent than any other period of life (Gee et al., 2016; Meyer et al., 2018). Due to this heightened expression of CB1R, the rodent brain is highly receptive to THC effects during adolescence (Heng et al., 2011). Similarly, in humans, CB1R expression peaks at ages 15-17 and declines to base levels near age 35 (Choi et al., 2012; Long et al., 2012), raising the possibility that adolescents are also at risk to heightened THC effects in humans. Notably, a recent report comparing responses to vaporized cannabis in adolescents vs adults indicated that adolescents reported *smaller* effects on certain subjective measures and less performance impairment. However, that study was complicated by possible differences in recent cannabis use and the fact that participants were not completely drug-free at the time of testing (Mokrysz et al., 2016). The purpose of the present study is to determine whether adolescence is a source of risk for THC intoxication in humans and to develop a new, sensitive behavioral assay to detect and compare THC effects. Greater sensitivity to acute THC intoxication may indicate higher potential for abuse, in addition to acute adverse effects including THC-induced psychosis and impairments in behavior and cognition.

Our central hypotheses are 1) that the subjective, behavioral, and physiological responses to acute THC will be greater in adolescents, including reductions in EEG activity during task performance, and 2) that speech and text analyses will be sensitive indices of acute THC intoxication across dose and age. We and others have used analysis of speech production to detect effects of drugs, using measures of both production and content (Baggott et al., 2015; Bedi et al., 2014). To our knowledge, speech and text analyses have not been used to study THC. Our hypotheses will be tested using a well-established regimen of oral 7.5 and 15 mg THC administration in the laboratory (Childs et al., 2017; Pabon and de Wit, 2019; Wardle et al., 2015).

**Significance & Innovation:** Cannabis use is widespread among adolescents and young adults with over 11 million people ages 18-25 having consumed cannabis in the past year (2015) in the United States (National Institute on Drug Abuse). Furthermore, the average age of onset is 19 years of age (National Survey on Drug Use and Health). Cannabis products are increasingly accessible to young adults in the United States, a trend tied to increased use (Ter Bogt et al., 2014). For example, after cannabis was legalized in Colorado in 2011, past year cannabis use increased from 39% to 49% for ages 18-25 through 2017 (National Survey on Drug Use and Health). The consequences of long-term cannabis use are more severe in adolescents, and there is evidence that chronic use of cannabis in adolescents is associated with impaired neural maturation (Chadwick et al., 2013; Coffey and Patton, 2016). However, it is not established whether adolescents are more or less sensitive to the short-term effects of acute THC intoxication. Preclinical studies consistently show that adolescent rats are more sensitive to the acute effects of THC than adult animals (Cha et al., 2006; Quinn et al., 2008; Wiley et al., 2007). The period of sensitivity coincides with a neurodevelopmental period when cannabinoid receptors are most densely expressed in both rodent and human cortex (Choi et al., 2012; Gee et al., 2016; Heng et al., 2011; Long et al., 2012; Meyer et al., 2018). Therefore, human adolescents may also be more sensitive to the acute effects of THC, and under certain circumstances this may increase their risk for adverse effects such as psychosis and behavioral impairments, or likelihood of abuse.

There is limited knowledge on the effects of THC in adolescents vs adults. One recent report compared responses to vaporized cannabis in heavy adolescent vs adult cannabis users (Mokrysz et al., 2016) and found that the adolescents were less sensitive to the drug on most measures. However, their findings were complicated by several factors: i) the study used vaporized cannabis, which may have other constituents and does not offer full control of the dose, ii) the participants were heavy users, making it difficult to determine the influence of prior drug exposure, and iii) the participants were not drug-free at the time of testing. Prior exposure to THC can lead to tolerance, and adolescents and adults may differ in the rate at which they develop tolerance, consistent with changes in CB1R receptor function (Burston et al., 2010; Cha et al., 2006; Murray, Pabon, de Wit, unpublished finding; Quinn et al., 2008; Wiley et al., 2007). Our study will compare adolescent (here, aged 18 to 20) and adult (here, aged 30 to 40) responses to THC in relatively light cannabis users who are drug-free at the time of testing.

A second goal of this study is to develop a sensitive measure of THC intoxication by analyzing text from samples of subjects' spontaneous speech. We have used analyses of speech production and semantic content to assess changes in mental state during acute intoxication with several other drugs, including MDMA and methamphetamine (Agurto et al., *in press*; Baggott et al., 2015; Bedi et al., 2014; Wardle et al., 2011), but never with THC. The application of speech and text analyses to THC effects is a promising avenue to develop more sensitive behavioral measures of THC intoxication. Importantly, the accurate detection of cannabis intoxication is a major public health concern. Drugs can change a range of features of human speech, including the quantity, speed, fluency, volume, and acoustic features. In addition, drugs can affect many aspects of semantic content including perceived features of drug effects. By applying sensitive quantitative techniques to analysis of speech and text samples, it may be possible to extract features that reflect intoxication with this drug.

A third goal is to determine whether THC alters EEG patterns, and whether this is related to age. THC is known to affect neural responses as measured by EEG from oscillatory power to evoked related potentials (ERP) (Skosnik et al., 2016). (For instance, oral, smoked, and intravenous administration of THC reduce the amplitude of the P300 waveform (D'Souza et al., 2012; Ilan et al.,

2005; Roser et al., 2008; Stadelmann et al., 2011; Theunissen et al., 2012). The P300 is a positive waveform that peaks 300 ms after a stimulus and is related to attention and working memory. Another study showed that vaporized THC (22 mg) reduced the error-related negativity (ERN) in frequent cannabis users. ERN is an ERP with negative polarity that corresponds to a participant's recognition of error during an error-monitoring task (Kowal et al., 2015). Although THC is known to disrupt gamma (30-80 Hz) and theta (4-7 Hz) oscillations (reviewed by Skosnik et al., 2016), in this study, we will focus specifically on the P300 and ERN. Electrophysiological measures are valuable because they provide a sensitive direct measure of neural activity and can be used to examine drug effects, and age-related variations in drug effects, in relation to both mood and cognitive performance.

**Research Design:** We will use a combined within and between subject design to examine whether healthy, young men and women (aged 18 to 20) are more sensitive than older participants (aged 30 to 40) to the acute effects of THC. Healthy occasional cannabis users in the two age groups will participate in three laboratory-based sessions spaced at least seven days apart, in which they will receive capsules containing placebo, 7.5 mg THC, or 15 mg THC under double-blind conditions. For each session, participants will complete self-report questionnaires of subjective effects, and cardiovascular measures will be obtained at regular intervals. They will complete speech, behavioral, and electroencephalogram (EEG) tasks once each session, at the time of expected peak effect.

**Participants.** Participants will include 20 healthy male and female volunteers, half of whom will be aged 18-20 and the other half aged 30 to 40. The N of 20 participants is based on a reported effect size ( $f = 0.403$ ; Mokrysz et al., 2016) on our primary outcome measure (group x drug interaction on Drug Effects Questionnaire: "Feel"), which requires a sample size of 16 for at least 80% power at an alpha of 5% (G\*Power). The groups will be matched on number of males and females and on body mass index. Subjects will be excluded if they have a history of psychosis, nursing or pregnant, planning to become pregnant, or have a body mass index outside of 19 to 26. Subjects must have at least a high school education and fluency in English. Other criteria include individuals who have used the drug between 1 to 20 times lifetime and 0 times in last 30 days. Qualifying participants will agree to abstain from alcohol for 24 hours and other recreational drugs for at least 2 days before each session. They will be informed that breath and urine samples will be obtained on each session to verify abstinence. Participants will also be asked to fast 4 hours before the behavioral laboratory session.

**Drug.** THC (Marinol® [dronabinol]; Solvay Pharmaceuticals) will be orally administered in doses of 7.5 mg and 15 mg, in opaque capsules with dextrose filler. Placebo capsules contain only dextrose. The 15 mg dose reflects the amount of THC in one-half of a cannabis cigarette containing 0.2 g of 15% THC. These doses of THC are known to produce performance impairments as well as subjective intoxication (Broyd et al., 2016; Hartman and Huestis, 2013; Pabon and de Wit, 2019).

**Orientation Session.** During an initial, 30-min orientation session, study procedures will be explained and participants will read and sign a consent form. Participants will then practice the tasks and questionnaires that will be administered during the subsequent study sessions. A urine sample will be obtained to confirm abstinence from cannabis; subjects will be instructed to maintain abstinence from cannabis throughout the study and refrain from any use of drugs or alcohol for 24 before and 6 hours after each drug administration session. Participants will also be told to have a normal night's sleep and to fast 4 hours before the session; a standardized snack will be provided.

Drug Administration Sessions. Three 5-hour drug administration sessions of placebo, 7.5 mg, or 15 mg Δ9-tetrahydrocannabinol (THC) will be separated by at least seven days. Each session will be conducted from 9 am to 1:30 pm in comfortably furnished study rooms that resemble living room settings. Upon arrival at the laboratory, participants will provide breath and urine samples to test for recent drug or alcohol use, and pregnancy (in females). Participants will complete the Addiction Research Center Inventory (ARCI) and Profile of Mood States (POMS) and provide measures for heart rate (HR) and Blood Pressure (BP) to assess their baseline state. Participants will consume a capsule containing 0, 7.5, or 15 mg THC under double-blind conditions. The order will be randomized across subjects. Participants will be provided a snack 30 min after administration. Participants will complete the ARCI, POMS, and Drug Effects Questionnaire (DEQ) 60, 120, 180, and 240 min after taking the capsule; heart rate (HR) and Blood Pressure (BP) will be taken at the same time. During peak drug effects, participants will complete a 10-min written self-report, 5-min monologue speech task and several behavioral tasks, including the Stop Task, N-Back Task, and Time Production Task (TPT) in randomized order. At 130 min post-administration, participants will be accompanied across the hall to the EEG center for two tasks: the Auditory Oddball P300 and Flanker Interference task. After EEG measures, participants will return to the lab and subjects will be given lunch. At 240 min subjects will complete the 5 Dimensions of Altered States of Consciousness (5D-ASC) scale, the State Mindfulness Scale (SMS) and an End of Session Questionnaire before being discharged. In the interest of safety, for subjects who cannot arrange a ride home, we will pay for transportation home. After the final session, participants will be informed of the purpose of the study including the drug that they received and will be allowed to ask any additional questions about the study.

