2. The Flanker Interference Task (Endrass et al., 2008; Eriksen and Eriksen, 1974) is an error monitoring task involving visual stimuli. A visual target stimulus is flanked by non-target stimuli that may either be congruent, incongruent, or neutral to the target response. Experimental stimuli will be displayed with Presentation software (Neurobehavioral Systems, San Francisco, CA) on an LCD monitor placed at a comfortable viewing angle. Trials begin with a fixation mark for 1100–1700 ms. 100 ms after onset of Flanker arrows, a central target arrow will appear for 30 ms. Subjects are to indicate the direction of the central target arrow with a button press. 500 trials will be presented, with 150 being compatible trials (with congruent flanker and target errors) and 350 being incompatible trials in pseudo-random order. To maintain time pressure and ensure an adequate number of error trials, subject response times will be recorded and subjects will be prompted to move more quickly based on a moving average of the past 50 correct trials. Error-related negativities (ERNs) will be recorded. This task takes 5 mins.

Timeline:

9:00	-30	Arrival, breath and urine tests
9:15	-15	Subjective and cardiovascular measures (baseline)
9:30	0	Capsule administration
10:00	+30	Standardized snack
10:30	+60	Subjective and cardiovascular measures
10:50	+80	Written self-report
11:00	+90	Subjective and cardiovascular measures, speech and behavioral tasks
11:30	+120	Subjective and cardiovascular measures
11:40	+130	Move to CNPRU and prepare EEG for recording
12:10	+160	EEG: auditory oddball P300 and Flanker task
12:30	+180	Subjective and cardiovascular measures
1:30	+240	Subjective and cardiovascular measures, 5D-ASC, SMS, End of Session Questionnaire

**Data Analyses:** The effects of the drug on subjective, behavioral, and cardiovascular measures will be assessed with mixed analysis of variance, with the between-subjects factor of group (adolescent, adult) and within-subjects factors of drug (placebo, 7.5 mg, 15 mg THC) and time (within session). Repeated measures ANOVA will compare ERPs including P300 amplitude between THC and placebo sessions.

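### Balancing of dose order within age group is not stated and the ANOVA has no session term, so any drift across sessions adds avoidable chance error to the primary age-by-drug contrast

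*Combined protocol and SAP*

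**What the plan says.** The Participants section sets the size and the primary test: "Participants will include 20 healthy male and female volunteers, half of whom will be aged 18-20 and the other half aged 30 to 40". The primary outcome is the "group x drug interaction on Drug Effects Questionnaire" item Feel. Research Design has "three laboratory-based sessions spaced at least seven days apart", one each for placebo, 7.5 mg and 15 mg, so six dose orders are possible.

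Allocation of those orders is covered by one sentence in Drug Administration Sessions: "The order will be randomized across subjects". No section mentions blocks, a list of sequences, counterbalancing of dose order or stratification by age. Balance between the age groups is specified for other things: "The groups will be matched on number of males and females and on body mass index".

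Data Analyses plans a mixed ANOVA "with the between-subjects factor of group (adolescent, adult) and within-subjects factors of drug (placebo, 7.5 mg, 15 mg THC"), plus time. That time factor is time since the capsule within a session. It is not session number, and neither session nor order appears in the model.

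**The concern.** Age is not randomised, so whether the two age groups receive similar dose orders depends entirely on the order list. Suppose one group happens to receive 15 mg later, relative to placebo, than the other. Any change in Feel ratings from session to session, such as habituation to the laboratory or expectancy after earlier doses, then enters the difference between the groups' THC effects. That difference is the trial's main result, it rests on 20 people, and the planned model contains nothing that would remove the drift.

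**Working it through.** **Inputs.** From the documents: 10 per age group, three conditions, six orders, and a model with group, drug and time within session. Not in the documents, so assumed: simple randomisation over the six orders; one Feel score per session with independent errors of within-subject SD 1; and a linear drift of *b* SD per session, taken from 0 to 1.

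**The plan's own figure.** Participants states that f = 0.403 "requires a sample size of 16 for at least 80% power at an alpha of 5"%. For a within-between interaction, λ = f²·N·m/(1−ρ). With two groups, m = 2 and ρ = 0.5 (both assumed), N = 16 gives λ = 0.1624 × 16 × 2/0.5 = 10.39 and power 0.850; N = 14 gives 0.790. The 16 is therefore reproduced, and power at N = 20 is 0.926. It does not depend on dose order. (The match uses two repeated measures where the design has three drug levels, which is a separate matter.)

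**Step 1: how unequal the orders can be.** Let *c* be the difference between age groups in mean (session of 15 mg − session of placebo).
- Over the six orders, one person's value is −2, −1, −1, 1, 1 or 2: mean 0, variance 12/6 = 2.
- Simple randomisation: Var(c) = 2/10 + 2/10 = 0.4, so SD = 0.63. The exact distribution gives P(|c| ≥ 0.5) = 48%, P(|c| ≥ 1) = 13% and P(c = 0) = 6%.
- Blocks of six within age group (one full block plus 4 of 6): the full block sums to 0. The other four have variance 4 × 2.4 × (1 − 4/6) = 3.2. Var(c) = 2 × 3.2/100 = 0.064, so SD = 0.25. By simulation, P(|c| ≥ 0.5) = 7%, and |c| ≥ 1 did not occur.
- Balancing over all 20 without regard to age: SD 0.65, P(|c| ≥ 0.5) = 50% (simulation). No gain.
- Same 10 orders in both groups: c = 0.

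**Step 2: effect on the contrast without a session term.** The group difference in (15 mg − placebo) has sampling variance 2/10 + 2/10 = 0.4. Drift adds b²·Var(c).

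| Drift *b* | SD, simple randomisation: √(0.4 + 0.4b²) | SD, blocks within age: √(0.4 + 0.064b²) |
|---|---|---|
| 0 | 0.63 | 0.63 |
| 0.25 | 0.65 | 0.64 |
| 0.5 | 0.71 | 0.64 |
| 1 | 0.89 | 0.68 |

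Simulation agrees (0.71 to 0.73 for simple randomisation at b = 0.5). The mean error was about 0 at every drift. Overall type I error was 0.048 to 0.051, but among allocations with |c| ≥ 1 it was about 0.07, 0.10 and 0.15 at b = 0.25, 0.5 and 1.

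**Step 3: power of the group-by-drug F test.** An effect of 1.8 SD on 15 mg in one group was chosen to give about 0.81 without drift: λ = 5 × 1.8² × 2/3 = 10.8 on 2 and 36 df. Under simple randomisation drift inflates the error variance by 1 + b², so λ becomes 10.8/1.25 = 8.64 at b = 0.5 and 10.8/2 = 5.4 at b = 1, which give power of about 0.71 and 0.50. Simulation, 4,000 trials per cell:

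| Order scheme | Session term | b = 0: power | b = 0.5: type I / power | b = 1: type I / power |
|---|---|---|---|---|
| Simple | no | 0.81 | 0.052 / 0.72 | 0.052 / 0.49 |
| Simple | yes | 0.78 | 0.050 / 0.79 | 0.048 / 0.80 |
| Blocks within age | no | 0.81 | 0.027 / 0.72 | 0.004 / 0.43 |
| Blocks within age | yes | 0.80 | 0.051 / 0.82 | 0.048 / 0.80 |
| Same list | no | 0.81 | 0.024 / 0.71 | 0.002 / 0.40 |
| Same list | yes | 0.81 | 0.054 / 0.81 | 0.051 / 0.82 |

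Balancing without a session term takes drift out of the estimate but leaves it in the error term, so the test becomes conservative and gains no power.

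**The case against.** The text is silent rather than adverse. One sentence saying that order is randomised across subjects is compatible with separate or counterbalanced lists. A reader might infer that the plan allocates order without regard to age; the documents do not say so. What stands is that balancing by age is not stated.

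A reader might also infer that unequal orders bias the age comparison or raise the false-positive rate. They do not: over randomisations the contrast is unbiased and type I error stays near 5%, whatever the drift. The harm is lost precision, and distortion conditional on a bad draw.

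The size rests on an assumption. A drift of 5 mm per session on the 100 mm scale would add 0.63 × 5 = 3.2 mm of SD. If the within-subject SD were 10, 20 or 30 mm, the total SD would rise by a factor √(1 + (5/SD)²), that is by about 12%, 3% or 1%. Nothing in the documents says which is nearer. Practice on the Stop and N-Back tasks does not bear on Feel, and participants rehearse tasks and questionnaires at the orientation session, which should reduce early familiarity effects.

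Finally, a session term under simple randomisation already restores most of the power (0.79 to 0.80), and balancing adds about 1 to 3 points. That is right for drift common to both ages. A shared session term does not fully remove drift that differs by age. For each 1 mm per session of age difference in drift, simulation leaves an error of SD 0.35 mm in the 15 mg contrast under simple randomisation, against 0.10 to 0.13 mm with blocks within age. The power gain there is also small: with drift of 0.5 SD in one group only, power was 0.74 as written and 0.77 with both changes.

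**Conclusion.** The point holds as one of efficiency and robustness: a cheap improvement. As written, and if simple randomisation is used, the age groups have about an even chance of differing by half a session or more in the relative position of 15 mg and placebo, and the planned model cannot remove the consequence. At an assumed drift of 0.5 within-subject SD per session this costs about 12% in the SD of the 15 mg contrast and about 9 points of power. At 1 SD it costs far more, and with no drift nothing. About one allocation in eight (13%) would be off by a full session or more, and there the type I error at a drift of 0.5 SD is about 0.10. The imbalance figures need only 10 per group and simple randomisation. The power figures also assume linear drift, independent errors and one score per session. Neither the validity of the test over all randomisations nor the stated requirement of 16 is affected.

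**What to change.** Make both changes together.

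1. In Drug Administration Sessions, replace the sentence on order with, for example: *Drug order will be randomised separately within each age group in balanced blocks of the six possible orders (last block incomplete), or the same list of 10 orders will be used in both groups in random sequence.* The final protocol should name one of the two. The shared list removes the between-group imbalance entirely unless people drop out.

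2. In Data Analyses, add session (1, 2, 3) as a within-subject term. Each person meets each drug in one session only, so session cannot be a further fully crossed factor. Fit it as a categorical term in a linear model with participant, drug and group-by-drug.

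Cost: two lists or one shared list, and two error degrees of freedom (36 to 34 in the one-score-per-session layout above). If there is no drift, power is essentially unchanged with balanced orders (0.80 to 0.81 against 0.81). Ten is not a multiple of six, so an incomplete block leaves slight residual imbalance and slight predictability. No extra participants or visits are needed.
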